13. Subject has clinically relevant abnormalities noted on renal ultrasound or DEXA scans. Subjects with baseline BMD Z-scores ≤ -2 , for either posterior-anterior lumbar spine (L1-L4) or total body less head, will not be enrolled.
14. Subject has congenital glaucoma or known ocular deficits, or is receiving any ocular medications except lubricating eye drops or topical antibiotics.
15. Subject has a known history of central hyperthermia, dysautonomia, or other disturbances of autonomic function.
16. Subject has a known history of inborn errors of metabolism, mitochondrial dysfunction, or prior evidence of hyperammonemia.

-
17. Subject has any clinically significant abnormality in laboratory tests at screening, including but not limited to:
 - WBC count $<3,000/\mu\text{L}$ or absolute neutrophil count $<1,000/\mu\text{L}$ in the last 6 months
 - Aspartate aminotransferase (AST), alanine aminotransferase (ALT), or gamma-glutamyltransferase (GGT) ≥ 3 times the ULN
 - Total bilirubin ≥ 1.5 mg/dL or conjugated bilirubin $\geq 20\%$ of total
 - Venous ammonia ≥ 2 times the ULN
 - 25-hydroxy-vitamin D (level for clinically significant vitamin D deficiency is <12.0 ng/mL, conventional units [<30 nmol/L, SI units])^{19,42}
 - Parathyroid hormone (normal reference range is 14.0 to 72.0 pg/mL)
 - 1,25-dihydroxy-vitamin D, as determined by the age-dependent reference ranges (see lab manual)
 - Insulin-like growth factor 1 (IGF-1), as determined by the age-dependent reference ranges (see lab manual)
 18. Subject has a bicarbonate level <20 mEq/L, has a diagnosis of metabolic acidosis, or is on alkali therapy.
 19. Subject has refractory epilepsy and requires adjunctive AED therapy or is receiving >1 concurrent AED (including benzodiazepines, regardless of the reason for prescription).
 20. Subject is being treated with furosemide, hydrochlorothiazide, vigabatrin, vitamin B₆ therapy for epilepsy, monoamine oxidase (A or B) inhibitors, felbamate, zonisamide, or any other medication that is a potent carbonic anhydrase inhibitor (eg, acetazolamide). Past treatment with furosemide for more than 2 weeks must be discussed with the sponsor and the discussion documented.

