A hand/wrist x-ray will be obtained in the nondominant hand/wrist to determine bone age at baseline and at Month 12 (or final study visit if a subject discontinues prematurely).²⁰ This will be read and interpreted locally.

Electrocardiogram

A single 12-lead ECG will be collected at screening only. To be enrolled, subjects must have an ECG at screening with no “abnormal, clinically significant” interpretations by a local cardiologist.

During the collection of ECGs, subjects should be in a quiet setting without distractions (eg, television, cell phones). Subjects should rest in a supine position for at least 5 minutes before ECG collection and should refrain from talking or moving arms or legs. If blood sampling or vital sign measurement is scheduled for the same time point as ECG recording, the procedures should be performed in the following order: ECG, vital signs, blood draw.

Vital Signs

Vital signs will be recorded at the times given in the Time and Events Schedule. Measurement of vital signs includes axillary temperature, heart rate, respiratory rate, and blood pressure. Temperature will be assessed using an axillary thermometer; if temperature is $\geq 38.0^{\circ}\text{C}$, the temperature should be repeated immediately and both values recorded in the CRF. Respiration measurements will be assessed over at least 30 seconds. Blood pressure and heart rate measurements should be assessed with a completely automated device (if available) consisting of an inflatable cuff and an oscillatory detection system. All values will be registered on a built-in recorder so that measurements are observer-independent. If an automated device is not available, all manual heart rate measurements will be measured each time for a full minute to minimize the effects of heart rate variability. Blood pressure will be measured with the cuff placed on the right arm. An appropriate size cuff has 1) an inflatable cuff bladder width that is at least 40% of the arm circumference (at a point midway between the olecranon and the acromion) and 2) a cuff bladder length that covers 80% to 100% of the circumference of the arm.

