10.2. Withdrawal From the Study

A subject will be withdrawn from the study for any of the following reasons:

- Lost to follow-up
- Withdrawal of consent
- The investigator or sponsor believes (eg, that for safety or tolerability reasons such as an adverse event) it is in the best interest of the subject to discontinue treatment.
- Death
- Other reasons
- If a female subject becomes pregnant during the study, she must be discontinued from the study and the pregnancy followed to term, if applicable.

During the study, subjects will also be withdrawn if:

- Subject develops status epilepticus not controlled by a single rescue agent.
- At the discretion of the investigator, subject develops any new seizure types or any clinically relevant safety issue.
- Subject requires greater than a 10-day course of medications that may impact bone metabolism, including intravenous or oral steroids, furosemide, growth hormone, NSAIDs, antacids, or calcium/vitamin D supplements.
- Subject develops nephrocalcinosis (diagnosed in any way) or develops a significant clinical adverse event (eg, serious event, treatment-limiting event, or other consideration) diagnosed as being related to a new kidney stone. Ultrasound results that suggest an asymptomatic kidney stone will not necessarily serve as a reason for withdrawal from the study.
- The investigator believes the subject to be at significant risk of suicidal or violent behavior.

If a subject discontinues treatment before the end of the open-label treatment phase, the end-of-study assessments should be obtained.

If a subject is lost to follow-up, every reasonable effort must be made by the study site personnel to contact the subject and determine the reason for discontinuation/withdrawal. The measures taken to follow-up must be documented.

When a subject withdraws before completing the study, the reason for withdrawal is to be documented in the CRF and in the source document. Study drug assigned to the withdrawn subject may not be assigned to another subject. Subjects who withdraw will not be replaced.

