2. If this model experiences convergence issues, then the same model with compound symmetric matrix followed by AR1 will be explored instead of unstructured.
3. If the above doesn't work, then a reduced model with treatment group, age group, visit, treatment-by-visit interaction, and baseline measure will be explored. Age will be collapsed to two categories: 2-9 years of age (pre-pubertal) and 10-15 years of age (pubertal). The unstructured covariance matrix will be explored first and if it doesn't work, then compound symmetric followed by AR1 will be applied.
4. If above doesn't work, then no additional MMRM analysis will be performed.

Sensitivity analyses:

Sensitivity analyses for height z-scores, weight-z-scores and BMD z-scores will be conducted for subset of safety analysis set: for subjects who started taking at least one concomitant AED, data collected after the start of taking AED medication will be excluded from the analysis.

Minor: 1. Insertion of correct schedule of events, 2. Addition of AED medication list in the Appendix, 3. Widening of screening window. 4. Age calculation at each visit for markedly abnormal labs and vital signs. 5. Update to SAS code for Vineland score calculation.

The overall reason for the amendment 2:

1. Widen the interval for DEXA scan to include 4 subject whose scans were done after baseline but within 1 month post-baseline
2. Calculate the exact age at each dosing visit
3. Total daily dose calculation for overlapping intervals: capped at their maximum allowed dose

The overall reason for the amendment 3:

1. Baseline is defined as the last non-missing observation (including an unscheduled visit) prior to or equal to Day 1 (except for DEXA and Bone age, where baseline includes up to 30 days and 180 days post-baseline, respectively).

CONFIDENTIAL – FOIA Exemptions Apply in U.S.

5

Status: Approved, Date: 08 June 2020

ABBREVIATIONS

AE	Adverse event
AED	anti-epileptic drug
ATC	Anatomical Therapeutic Chemical
BMC	bone mineral content
BMD	bone mineral density
BMDCS	Bone Mineral Density in Childhood Study
BMI	Body Mass Index
CBCL	Child Behavior Checklist
CDC	Centers for Disease Control
CI	confidence interval
CRF	case report form
C-SSRS	Columbia-Suicide Severity Rating Scale
DEXA	dual energy x-ray absorptiometry
DMC	data monitoring committee
IWRS	interactive web-based response system
MedDRA	Medical Dictionary for Regulatory Activities
MMRM	Mixed Model Repeated Measures
PGTCS	primary generalized tonic-clonic seizures

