^b There may be an optional post-study follow-up phase to obtain DEXA measurements in a subgroup of subjects who experience a clinically important reduction (change in Z-score of -0.5 or greater) in BMD, based on local DEXA scan results, after 1 year of treatment with topiramate; these subjects will have a repeat DEXA scan 6 months after discontinuation of study drug.

^c The Day 1 visit will serve as the baseline visit. All procedures on Day 1 (except dispensing of study drug) should be completed before randomization.

^d The site will contact the subject via telephone at Month 13, to collect data on adverse events and concomitant medications.

^e Window for all visits will be ±7 days.

^f Adequacy of physical activity will be assessed with the Habitual Activity Estimation Scale.

^g Investigator will document inadequacy of any epilepsy treatment that the subject is receiving at the time of screening. Information regarding AED use and other medications within 2 years prior to the study will also be collected.

- ^h If possible, blood samples for determination of plasma topiramate and levetiracetam concentrations should be trough samples (taken immediately before the morning dose) and should coincide with samples drawn for clinical laboratory tests.
- ⁱ Subjects will be weighed in examination gowns or in lightweight clothing and without shoes. Height will be assessed using a wall-mounted stadiometer. All study site personnel measuring height will be blinded to treatment to avoid/minimize bias.
- ^j Orthostatic vital signs will be obtained for all subjects pending cooperation of subjects. A set of 3 measurements will be obtained at baseline only at intervals of 10 minutes. Thereafter, only 1 orthostatic vital sign measurement will be taken at all subsequent visits. The method for obtaining orthostatic vital signs will be as follows: subject will be supine for 5 minutes prior to measurement, and standing for 2 minutes prior to measurement.

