5	Month 3	76 to 135	90
6	Month 6	136 to 225	180
7	Month 9	226 to 315	270
8	Month 12	>=316	360

^a The randomization day is Day 1.

The analysis windows for DEXA is given in [Table 8](#).

Table 8: Definition of windows for DEXA:

Scheduled Visit Number	Time Interval (label on output)	Time Interval (Day) ^a	Target Time Point
1, 2	Baseline	-35 to 30	1
6	Month 6	31 to 270	180
8	Month 12	>=271	360

^a The randomization day is Day 1.

The analysis windows for Pharmacokinetics is given in [Table 9](#).

Table 9: Definition of windows for Pharmacokinetics

Scheduled Visit Number	Time Interval (label on output)	Time Interval (Day) ^a	Target Time Point
3	Month 1	2 to 45	30
5	Month 3	46 to 135	90
6	Month 6	136 to 270	180
8	Month 12	>=271	360

^a: The randomization day is Day 1

Baseline is defined as the last non-missing observation (including an unscheduled visit) prior to or equal to Day 1 (except for DEXA and Bone age, where baseline includes up to 30 days and 180 days post-baseline, respectively).

For post baseline observations, if more than one visit (including an unscheduled visit) occurs in the same time window, the visit nearest to the target day will be used in the analysis. In the case of an equal distance in time, the latest visit will be used.

Data that are not used in the analysis due to multiple observations or being excluded from the above defined time intervals will be displayed in the data listing.

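### SAP 3.1 sets no priority for the pre-treatment scan, leaves early-withdrawal bone-age and DEXA scans without a change value, and gives post-study DEXA no row of its own

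*SAP*

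**What the plan says.** **Baseline.** SAP 3.1 states the general rule: "Baseline is defined as the last non-missing observation (including an unscheduled visit) prior to or equal to Day 1". It then makes an exception: "except for DEXA and Bone age, where baseline includes up to 30 days and 180 days post-baseline, respectively". The Baseline rows agree with this: Day -35 to 180 in Table 6 (bone age) and Day -35 to 30 in Table 8 (DEXA). Where several post-baseline observations share a window, "the visit nearest to the target day will be used in the analysis", with ties going to the later visit.

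**Reason for the extension.** The SAP Amendment History, under amendment 2, gives it for DEXA only: "Widen the interval for DEXA scan to include 4 subject whose scans were done after baseline but within 1 month post-baseline". No reason is given for 180 days for bone age.

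**Pre-treatment scans.** SAP Table 1, footnote c: "All procedures on Day 1 (except dispensing of study drug) should be completed before randomization". Protocol 4.2, criterion 13, uses the baseline BMD Z-score to exclude children. Protocol 6 puts the first dose in the evening of Day 1, so scans from Day 2 are on treatment.

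**Withdrawal scans.** Protocol 10.2: "If a subject discontinues treatment before the end of the open-label treatment phase, the end-of-study assessments should be obtained". Protocol 9.3 schedules the bone-age X-ray at baseline and at Month 12 or the final visit, and DEXA at baseline, Month 6 and Month 12 or early withdrawal.

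**Post-baseline windows.** Table 6 has one: Month 12, from Day 181. Table 8 has two: Month 6 (Days 31 to 270) and Month 12 (Day 271 onward, no upper limit).

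**Repeat DEXA.** Protocol 3.1 and SAP Table 1, footnote b, offer a repeat scan 6 months after stopping to children with a BMD Z-score drop after 1 year of topiramate, based on local reads. SAP 7.4 triggers the repeat on a drop at 6 or 12 months and names no arm. Neither Table 8 nor SAP 7.4 gives that scan a window.

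**The concern.** An extension made for 4 children is written as a rule for every child, and it is not limited to children who lack a scan on or before Day 1. Combined with the last-observation rule, it lets an on-treatment value stand as baseline.

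The windows cause a second loss, whichever scan is called baseline. A child with a valid Day 1 X-ray who withdraws on Day 150 and has the required final X-ray contributes no change in bone age. Bone maturation and mineralization belong to the primary objective, and descriptive summaries by visit are the main analysis, so these children disappear from the summary of interest.

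Third, SAP 1 names change in BMD Z-score at Month 12 as a key endpoint and shows that repeat scans were still expected. With no upper limit on Month 12 and no follow-up row, a scan taken 6 months after study drug was stopped could be counted as an on-study value, and only for children selected for a BMD drop. The direction of any bias is unknown: children may continue on commercial drug, and recovery is the open question.

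**Working it through.** **1. Apply the rules as written.** Baseline is the last scan in the Baseline window. A post-baseline value is the scan nearest to target, the later one if tied.

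| Scan days | Baseline | Post-baseline value |
|---|---|---|
| DEXA 1, 20 | 20 | none |
| DEXA 1, 31 | 1 | Month 6 = Day 31 |
| Bone age 1, 150 | 150 | none |
| Bone age 1, 181 | 1 | Month 12 = Day 181 |

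If Day 1 is instead kept as baseline in the first and third rows, the Day 20 and Day 150 scans still have no window. The loss therefore does not depend on how baseline priority is read. Tables 2 to 5 do not share this gap: their first post-baseline window opens on Day 2.

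**2. How many children withdraw in those periods.** The inputs are the 1-year dropout of 29% and the 22% and 35% cited with it (SAP 2.4). The plan's own figure reproduces: 100/(1 - 0.29) = 140.8, so 141 per arm and 282 in all. The timing of dropout is not given, so I assume a constant hazard: P(withdraw by day t) = 1 - (1 - d)^(t/365).

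- By Day 180: 1 - 0.71^(180/365) = 0.155 (0.115 at 22%; 0.191 at 35%).
- By Day 30: 1 - 0.71^(30/365) = 0.028 (0.020; 0.035).

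On the planned 282 this is about 44 children for bone age and 8 for DEXA. Enrollment stopped early, so the percentages are the better guide. Only those who have a withdrawal scan are affected.

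**3. Where a repeat DEXA lands.** Take the repeat at stop day S + 180, with a withdrawal scan on Day S.

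- S = 31: the repeat is on Day 211, 31 days from target Day 180; the withdrawal scan is 149 days away. The repeat becomes Month 6.
- S = 90: the repeat is on Day 270. Both scans are 90 days from target, and the later one is used.
- S = 91: the repeat is on Day 271 and becomes Month 12. The same holds up to S = 270 (repeat on Day 450).
- S = 271: the withdrawal scan is 89 days from Day 360 and the repeat 91. The withdrawal scan is kept.

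A completer with scans on Days 180, 360 and 540 keeps Day 360 as Month 12.

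**4. Size of step 3, only if the SAP 7.4 trigger is applied.** Assume mean BMD Z-score change 0 and the annual SD of 0.4 from SAP 2.4 (range 0.3 to 0.48), with every eligible child in both arms rescanned.

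- Stops on Days 91 to 270: 0.71^(90/365) - 0.71^(270/365) = 0.919 - 0.776 = 0.143.
- Drop of 0.5 or more: Phi(-0.5/0.4) = 0.106.
- Children affected: 0.143 x 0.106 = 0.0151.
- Share of Month 12 values: 0.0151/(0.7762 + 0.0151) = 1.9%.
- Range, pairing low dropout with low SD and high with high: 0.6% to 3.4%.

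If the SD instead grows with the square root of exposure time (a further assumption), the share is 0.7% (0.1% to 1.5%).

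**The case against.** **Baseline wording.** The exception can be read as a fallback for a missing pre-treatment scan. The stated purpose of 4 late-scanned children supports that. The SAP also calls the added days post-baseline, and the Baseline rows carry a target of Day 1, so one could argue that the nearest-to-target rule favors the Day 1 scan. The second argument is strained, because a Day 1 scan is not itself a post-baseline observation. Still, displacement of the Day 1 scan is the literal reading and not the only one. A reader might infer that the SAP intends to replace valid Day 1 scans; the documents do not show that.

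**Dilution.** A reader might also infer that late DEXA baselines materially shrink the annual change. A child whose withdrawal scan becomes baseline has no change to shrink, and the 4 late-scanned children keep a late baseline under any sensible fix. The schedule has no other DEXA between Day 1 and Day 30, and no such scan is reported.

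**DEXA before Day 31.** Protocol 16.1 cites a 6-month minimum interval for repeating BMD measurement, so leaving a scan by Day 30 out of the visit summaries is defensible. This stands for the Month 6 row. It does not explain why the value is reported in no change summary at all, and it says nothing about bone age.

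**Post-study scans.** SAP 1 says that remaining children are followed according to the protocol. Under the protocol trigger, a completer is affected only without a usable Month 12 scan. The follow-up phase is also optional and needs separate consent. So a reader who infers routine contamination of Month 12 BMD goes too far. The 1.9% is not a general bound either: mean change 0 rests on data from healthy children.

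**Consequence.** No formal testing is planned, the MMRM is a sensitivity analysis, bone age is descriptive, and unused scans are listed. All of this stands and limits the stakes.

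**Conclusion.** The point holds as a defect in the data rules that should be fixed, with limited consequence.

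- **Certain from the text:** withdrawal X-rays up to Day 180 and withdrawal DEXA scans up to Day 30 have no post-baseline window and give no change value. The repeat-scan triggers in SAP 7.4 and in the protocol with footnote b conflict. Table 8 has no follow-up row.
- **Literal but not the only reading:** an on-treatment scan replaces a valid Day 1 scan as baseline.
- **Size:** bone age is the main loss, with about 15.5% of children withdrawing by Day 180 (11.5% to 19.1%). DEXA is minor, at about 2.8% by Day 30 (2.0% to 3.5%). Both rest on the constant-hazard assumption, and only children with a withdrawal scan count.
- **Post-study scans at Month 12:** about 1.9% of values (0.6% to 3.4%), but only under the SAP 7.4 trigger, with mean BMD Z-score change 0 and every eligible child rescanned. Under the protocol trigger this is rare.

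**What to change.** 1. **Baseline.** State in SAP 3.1 that baseline is the last scan on or before Day 1. Use a later scan inside the window only if none exists and it is not a withdrawal scan, and flag it. The 4 late-scanned DEXA children keep a flagged baseline.
2. **Final-visit row.** Add an early-withdrawal/final-visit row to Tables 6 and 8, reporting change from that baseline with the study day shown. Keep DEXA changes up to Day 30 in that row only. Item 1 alone is not enough, because the windows also have to accept these scans.
3. **Follow-up row.** Exclude scans collected as post-study repeats, 6 months after discontinuation, from the Month 6 and Month 12 DEXA rows and report them in their own row. Identify them by study phase. A cut-off at the end-of-study visit date could discard a genuine Month 12 or withdrawal scan done a few days late.
4. **Trigger.** Reconcile SAP 7.4 with the protocol and SAP Table 1, footnote b, on when the repeat scan applies and in which arm.

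The cost is SAP wording, new table rows and derivation code. No new data are needed.

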Information regarding physical activity will be obtained at screening from the HAES (see [Attachment 1](#) for an example). Parents/caregivers will be asked how many hours their children spent in a 24-hour day in 1 of 4 categories of activity/inactivity to assess physical activity levels on the basis of the standardized and validated activity questionnaire. The total number of hours each subject spends in each category will be processed to determine the activity score on a scale of -100 (100% inactive) to +100 (100% active). A value of 0 indicates that the subject spent 12 hours of the day active and an equal number of hours inactive.²²

Renal Stone Evaluation

Renal ultrasounds (at screening, Month 6, and Month 12/early withdrawal; without sedation and after a 3-hour period during which only water, juice, or electrolyte solution will be permitted, as clinically indicated) will be performed under blinded conditions (after randomization) by a qualified radiologist or nephrologist at each site with age-appropriate inducers. The ultrasounds will be read/interpreted centrally (local reading at the screening visit is acceptable to determine eligibility for randomization; both the local and central readers will be blinded to the study treatment group). If possible, examinations should be done by the same individual at any given site.

Subjects with definite renal stones, nephrocalcinosis, or hydronephrosis at screening will be excluded from the study. Other abnormalities will be followed in subsequent examinations, which may occur more frequently at the discretion of the investigator in collaboration with the sponsor's medical monitor. Abnormalities will be reported to parents and primary-care physicians, and appropriate referrals will be made by the investigator if needed.

Cognitive, Developmental, and Behavioral Assessments

Cognitive, developmental, and behavioral assessments will be conducted as follows:

- Cogstate Battery (2 practice sessions, 1 at screening and 1 baseline prior to the baseline assessment; assessed at baseline, Month 6, and Month 12/early withdrawal):
 - ◊ For subjects 6 to 15 years of age, the Detection Test, Identification Test, One Card Learning Test, One Back Test, and Groton Maze Learning Test will be administered.
 - ◊ For cooperative subjects 4 to 5 years of age, the Detection Test and the Identification Test will be administered.

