3.1. Visit Windows

The statistical analysis for safety will be based on time intervals that are constructed according to the number of days in trial from day 1. (See table 2-8)

The analysis windows for height, weight, exposure, vital signs, laboratory tests, physical examination and neurological examinations is given in [Table 2](#).

Table 2: Definition of windows for height, weight, exposure, vital signs, laboratory tests, physical examination and neurological examinations:

Scheduled Visit Number	Time Interval (label on output)	Time Interval (Day) ^a	Target Time Point
1,2	Baseline	-35 to 1	1
3	Month 1	2 to 60	30
5	Month 3	61 to 135	90
6	Month 6	136 to 225	180
7	Month 9	226 to 315	270
8	Month 12	≥ 316	360

^a The randomization day is Day 1.

The analysis windows for Renal Ultrasound, Cogstate, Tanner Staging and 24 hour urine collection is given in [Table 3](#).

Table 3: Definition of windows for Renal Ultrasound, Cogstate, Tanner Staging and 24 hour urine collection:

Scheduled Visit Number	Time Interval (label on output)	Time Interval (Day) ^a	Target Time Point
1, 2	Baseline	-35 to 1	1
6	Month 6	2 to 270	180
8	Month 12	≥ 271	360

^a The randomization day is Day 1.

The analysis windows for C-SSRS is given in [Table 4](#).

Table 4: Definition of windows for C-SSRS:

Scheduled Visit Number	Time Interval (label on output)	Time Interval (Day) ^a	Target Time Point
1, 2	Baseline	-35 to 1	1
3	Month 1	2 to 45	30
4	Month 2	46 to 75	60
5	Month 3	76 to 135	90
6	Month 6	136 to 225	180
7	Month 9	226 to 315	270
8	Month 12	>=316	360

^a The randomization day is Day 1.

The analysis windows for Vineland Scale and CBCL is given in [Table 5](#).

Table 5: Definition of windows for Vineland Scale and CBCL:

Scheduled Visit Number	Time Interval (label on output)	Time Interval (Day) ^a	Target Time Point
1, 2	Baseline	-35 to 1	1
5	Month 3	2 to 135	90
6	Month 6	136 to 270	180
8	Month 12	>=271	360

^a The randomization day is Day 1.

The analysis windows for Bone Age is given in [Table 6](#).

Table 6: Definition of windows for Bone age:

Scheduled Visit Number	Time Interval (label on output)	Time Interval (Day) ^a	Target Time Point
1	Baseline	-35 to 180	1
8	Month 12	>=181	360

^a The randomization day is Day 1.

The analysis windows for seizure count is given in [Table 7](#).

Table 7: Definition of windows for seizure count:

Scheduled Visit Number	Time Interval (label on output)	Time Interval (Day) ^a	Target Time Point
3	Month 1	2 to 45	30
4	Month 2	46 to 75	60

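### Read literally, the one-scan-per-window rule can leave an early-withdrawal or unscheduled renal ultrasound out of the kidney stone percentage

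*SAP*

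**What the plan says.** - **Scope of the windows.** SAP 3.1 opens with "The statistical analysis for safety will be based on time intervals", counted in days from Day 1. Table 3 carries the title "Definition of windows for Renal Ultrasound, Cogstate, Tanner Staging and 24 hour urine collection". After baseline it has two rows: Month 6 (Days 2 to 270, target 180) and Month 12 (Day 271 or later, target 360).
- **Choice within a window.** For post-baseline data, when several visits share a window, unscheduled ones included, "the visit nearest to the target day will be used in the analysis". On ties, "In the case of an equal distance in time, the latest visit will be used".
- **Fate of the other scans.** "Data that are not used in the analysis due to multiple observations or being excluded from the above defined time intervals will be displayed" in a listing.
- **The stone analysis.** SAP 7.1 asks for the proportion of children in each arm with stones, or with ultrasound findings pointing to stones, plus a listing. It does not say which scans feed the proportion.
- **Withdrawal scans.** Protocol 10.2: "If a subject discontinues treatment before the end of the open-label treatment phase, the end-of-study assessments should be obtained". The Time and Events Schedule puts a renal ultrasound among those assessments. The same section withdraws a child who develops nephrocalcinosis or an important clinical event attributed to a new stone. It adds that a symptom-free stone on ultrasound need not lead to withdrawal.
- **Extra scans.** Protocol 9.3 has abnormalities other than the excluding ones followed in later examinations, "which may occur more frequently at the discretion of the investigator".

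**The concern.** Picking the visit nearest to target suits a by-visit mean, where each child should contribute one value at a comparable time. Whether a child ever formed a stone is a different kind of outcome: one positive scan settles it, and a clear scan on another day does not cancel it. If only the scan nearest target counts, a child who is clear at Month 6 and positive at withdrawal in Month 8 is reported as stone-free.

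Stone formation is part of the primary objective in Protocol 2.1 and a secondary objective in SAP 2.1. SAP 7 plans no formal testing, so this percentage is the main ultrasound result. The Protocol 11.2 planning values put stones almost entirely in the topiramate arm, so under those values any lost case pulls the comparison towards no difference.

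**Working it through.** **1. The plan's own figure.** Inputs from Protocol 11.2 (SAP 2.4 no longer carries the stone item): 7% versus near zero, 100 completers per arm, Wilson score interval for the difference, stated width 0.12.

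Wilson limits for one proportion, with z = 1.96: [p + z²/2n ± z√(p(1−p)/n + z²/4n²)] / (1 + z²/n).
- 7/100: 0.0343 to 0.1375.
- 0/100: 0 to 0.0370.
- Lower limit of the difference: 0.07 − √[(0.07 − 0.0343)² + 0.0370²] = 0.0186.
- Upper limit: 0.07 + (0.1375 − 0.07) = 0.1375.
- Width: 0.1189, which rounds to 0.12. Reproduced.

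The randomized number also reproduces: 100/(1 − 0.29) = 140.8, so 141 per arm and 282 in all.

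**2. The SAP 3.1 rule applied to example scan days.**

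| Scan days | Kept for analysis | Left out |
|---|---|---|
| 180, 240 | 180 (distance 0 v 60) | 240 |
| 120, 180 | 180 | 120 |
| 180, 270 | 180 | 270 |
| 180, 271 | both (Month 6, Month 12) | none |
| 180, 300 | both | none |
| 180, 300, 360 | 180 and 360 | 300 |
| 173, 185 | 185 (distance 5 v 7) | 173 |
| 173, 187 | 187 (tie, later wins) | 173 |
| 240 only | 240 | none |

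Allocation is by study day, so giving a Day 240 withdrawal scan the end-of-study visit number does not move it to Month 12.

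**3. Direction.** SAP 3 in general divides by the number of subjects in the analysis population, so the denominator does not depend on which scans are kept. The kept scans are a subset of all post-baseline scans. The number positive on kept scans therefore cannot exceed the number positive on any scan, and the rule can only lower the percentage or leave it unchanged.

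**4. How many children could be exposed.** The documents give a 29% one-year dropout (source rates 22% and 35%) but not its timing. Assume a constant hazard, with the proportion remaining S(t) = 0.71^(t/360):
- Days 181 to 270: S(180) − S(270) = 0.8426 − 0.7735 = 0.0691, × 141 = 9.7 per arm.
- Days 271 to 360: 0.7735 − 0.71 = 0.0635, × 141 = 8.9 per arm.

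Uniform timing gives 0.29/4 × 141 = 10.2 in each quarter. Across 22% to 35% dropout and both timing assumptions, about 7.5 to 12 children per arm withdraw on Days 181 to 270. So about half (50% to 53%) of withdrawals after Month 6 fall where the rule can displace their scan. These are children with a displaced scan, not children with a lost stone. Unscheduled scans come on top and cannot be estimated.

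**5. Illustration of the effect.** Let k of the 7 planned cases be visible only on a displaced scan, with 0/100 in the other arm:

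| k | Difference | 95% interval |
|---|---|---|
| 0 | 0.07 | 0.019 to 0.137 |
| 1 | 0.06 | 0.011 to 0.125 |
| 2 | 0.05 | 0.003 to 0.112 |
| 3 | 0.04 | −0.004 to 0.098 |

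The documents do not give k. The 100 per arm is a completer figure, whereas withdrawal scans come from non-completers, so the table shows sensitivity and is not a forecast.

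**The case against.** The strongest reply is that SAP 7.1 does not describe a by-visit summary. Sections 7.2 to 7.7 summarize by visit, and 7.1 does not. A subject-level percentage can be read as ever/never already, in which case nothing is lost. This stands in part: the reach of the rule is arguable. But 7.1 is the SAP's only summary of ultrasound findings, so if the windows do not feed it, naming renal ultrasound in Table 3 serves no purpose. Where the SAP wants any-time counting it says so, as for markedly abnormal laboratory values (7.10) and the C-SSRS (7.13). Kidney stones have no such sentence.

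Second, a child withdrawn for a stone event also has an adverse event. SAP 7.9 tabulates kidney stones as an event of special interest, Appendix 3 includes nephrolithiasis and nephrocalcinosis, and every scan finding is listed. This stands, so the case would not vanish from the report. However, adverse events are reported by investigators who know the treatment, whereas the ultrasound is read centrally and blinded to avoid that problem. Listings do not enter the percentage.

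Third, a reader might infer that a withdrawal scan is discarded whenever a Month 6 scan exists, and that the discarded scans are those most likely to show a stone. The documents do not support either statement. Scans from Day 271 go to Month 12, and a later scan as near or nearer to Day 180 replaces the Month 6 scan. Positive selection is an inference: symptom-free stones need not cause withdrawal, the stones in the infant extension study were mostly symptom-free (Protocol 1), and children withdraw for many other reasons. The extra-scan sentence in Protocol 9.3 concerns other abnormalities. A stone already visible on the retained scan is still counted, and the infant data in Protocol 16.1 place detection at about 4 to 5 months, before Month 6.

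**Conclusion.** The point holds in limited form. As written, SAP 3.1 can exclude a centrally read positive scan from the stone percentage, nothing in 7.1 prevents it, and any error is downward. The exposed scans are withdrawal scans on about Days 181 to 270 after a Month 6 scan, and unscheduled scans further from target in either window. The Protocol 10.2 withdrawal criteria make these plausibly, not demonstrably, more often positive.

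The size cannot be derived. Roughly 10 children per arm would have a displaced withdrawal scan at the planned 141, if the 29% dropout is spread evenly or at a constant hazard and the scheduled scans are done. SAP 1 records that enrolment stopped early, so the arms are smaller than planned; fewer children would be exposed, but each lost case would move the percentage more. At planning values two lost cases take the difference from 0.07 to 0.05. The result affected is descriptive, so this is a change that should be made rather than a flaw that undermines the trial.

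**What to change.** 1. In SAP 7.1, state that a child counts as positive if any post-baseline, centrally read renal ultrasound up to the end-of-treatment visit shows a stone, including early-withdrawal and unscheduled scans.
2. In SAP 3.1, limit the nearest-visit rule to by-visit summaries.
3. Add a sensitivity count that uses only scheduled and early-withdrawal scans.

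The third item covers the small downside of the first. Treatment is open-label and extra scans are discretionary, so one arm may be scanned more often and have more stones found for that reason alone. If the two counts agree, the concern falls away; if they differ, the reader can see by how much. The cost is two or three sentences in the SAP, a minor programming change and one extra table row. No additional data are needed.
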